9.7.3 Interim Analysis

One interim analysis will be performed after the first 20 evaluable subjects complete at least 2 tumor assessments or discontinue treatment due to any reason. The trial will be halted if the number of responders is 3 or less ($ORR \leq 15\%$). Since type I error calculation for the primary efficacy analysis does not factor in this descriptive interim analysis, the interim decision will not affect the overall type I error in the formal primary analysis. Further action regarding enrollment will be taken after evaluating other efficacy and safety outcomes in the treated subjects. The probabilities of not passing interim threshold are 0.87, 0.41, and 0.17 when underlying true ORR are 10%, 20%, and 27%, respectively.

The study team will define the datasets for the interim analysis. The study team will assess the impact of any issues such as unsolved data queries, missing data or data entry delays on

the interim results. The study statistician will perform the interim analysis, which includes calculating ORR per protocol.

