9.5.1.3.1 TUMOR ASSESSMENTS

Tumor assessments will be performed using RECIST 1.1. Assessments are to be performed at the site by appropriately qualified personnel at each time point and results of the site interpretation are to be recorded on the appropriate CRFs. Historical standard of care scans that are performed with scanning parameters consistent with the requirements for this protocol within 21 days prior to dosing are acceptable. Tumor assessments (CT chest and CT/MRI of neck, abdomen, pelvis, and other areas of known disease at screening plus any areas of newly suspected disease) should be performed at screening, every 6 weeks \pm 1 week

for the first 24 weeks and every 8 weeks \pm 1 week thereafter, or sooner if clinically indicated, until documentation of disease progression. A bone scan and brain scan will be performed within 21 days prior to C1D1, and continuing from C1D1 every 24 weeks \pm 1 week, or as clinically indicated. If PET/CT is performed, a bone scan is not necessary. In addition, for subjects with a history of treated brain metastases, brain scans will be performed at tumor assessment time points, if clinically indicated. In subjects with CR based on body CT/MRI scans, a bone scan (or PET/CT, if performed at Screening) and brain scan assessment will be required at response confirmation. All objective responses must be confirmed at least 28 days following the initial achievement of the response.

The CT scan should be a diagnostic quality spiral or multidetector CT with oral and iodinated IV contrast, and the MRI scan should be performed with IV gadolinium chelate. Scans of the neck, abdomen, pelvis, and other areas of the body may be done with MRI instead of CT, but evaluation of the chest must be done with CT. If iodinated IV contrast is contraindicated, the chest evaluation should be done with non-contrast CT, and the abdomen and pelvis evaluation should be performed using either CT with oral contrast (without IV contrast) or MRI with gadolinium chelate IV contrast (the latter is preferred). Spiral/multidetector CT should be performed with a 5-mm contiguous slice reconstruction algorithm. If body MRI scans are performed, contiguous slices of 5 mm are also recommended.

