#### 5.1.1 Primary Endpoint

The primary efficacy endpoint is ORR as determined by investigator review, using RECIST 1.1. ORR is the proportion of subjects who have best overall response (BOR) of CR or PR (confirmed). Confirmation of CR or PR must be performed at least 28 days following the initial achievement of the response.

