## 6 INTERIM ANALYSES

Per study protocol, one interim analysis was planned to be performed after the first 20 evaluable subjects complete at least 2 tumor assessments or discontinue treatment due to any reason. From the interim analysis the enrollment would be halted if the number of responders is 3 or less ( $ORR \leq 15\%$ ), and the safety and efficacy data would be further evaluated before making the decision of stopping the study permanently.

The study team would define the datasets for the interim analysis. The study team would assess the impact of any issues such as unsolved data queries, missing data or data entry delays on the interim results. The study statistician would perform the interim analysis, which would include calculating ORR per protocol.

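### The interim counts confirmed responses but can be taken before responses first seen at a second scan can be confirmed, so the stated 0.17 chance of missing the threshold at a true ORR of 27% is somewhat too low.

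*Protocol*

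**What the plan says.** Protocol 9.7.3 sets the timing: the one interim look comes "after the first 20 evaluable subjects complete at least 2 tumor assessments or discontinue treatment due to any reason". For the decision, the rule is "The trial will be halted if the number of responders is 3 or less" out of those 20. On what is computed: "The study statistician will perform the interim analysis, which includes calculating ORR per protocol"; SAP section 6 repeats this ("which would include calculating ORR per protocol"). The operating characteristics are given as: "The probabilities of not passing interim threshold are 0.87, 0.41, and 0.17 when underlying true ORR are 10%, 20%, and 27%, respectively".

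Per protocol, ORR is the proportion with a best overall response of CR or PR (9.7.1.1.1), and that requires confirmation. Protocol 9.5.1.3.1: "All objective responses must be confirmed at least 28 days following the initial achievement of the response". SAP 5.1.1: "Confirmation of CR or PR must be performed at least 28 days following the initial achievement of the response". Appendix 2 ties the assignment of best overall response to the same 4-week minimum. Subjects with missing data count as non-responders (Protocol 9.7.1.9; SAP 5.3.5). Neither interim section exempts the interim tally from confirmation.

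Scans are every 6 weeks ±1 week for the first 24 weeks (9.5.1.3.1; Table 4, footnote u). Post-baseline scans 1, 2 and 3 therefore fall at about weeks 6, 12 and 18.

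**The concern.** The trigger and the endpoint do not fit together. A response first seen at week 6 can be confirmed at week 12. One first seen at week 12 is normally confirmed at week 18, after the minimum trigger has already been met for that subject. The last subjects to enter among the 20 can therefore carry responses that will later be confirmed but are scored as non-responses at the look.

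The trigger also treats a subject as ready once treatment stops. Yet the protocol continues scans off treatment until progression or new therapy, so a pending response in such a subject could still be confirmed.

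The threshold of 3 of 20 is thus applied to an incomplete count, while its error rates were worked out for a complete one. It is the only quantitative interim rule in the plan. Those acting on it would believe that an active drug at the design ORR has a 17% chance of missing the threshold, when the chance is higher.

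**Working it through.** **1. The plan's figures.** For X ~ Binomial(20, p), P(X ≤ 3) is 0.867 at p = 0.10, 0.411 at 0.20 and 0.170 at 0.27. All three stated values reproduce. The calculation gives each of the 20 subjects the full ORR, so it contains no response that is still awaiting confirmation.

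**2. How many subjects are affected.** Planned accrual is 57 evaluable subjects (9.7.2) over 18 months (Synopsis, Study Period): 57/18 = 3.17 per month. Six weeks is 42/30.44 = 1.38 months, so about 3.17 × 1.38 = 4.4 subjects enter in the 6 weeks before the 20th. Adding the 20th gives about 5.4 of 20 who have not reached scan 3 when the 20th has scan 2.

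**3. The adjusted probability.** Let f be the share of eventual confirmed responders first seen at scan 1, with the rest at scan 2. The documents do not give f; I use 0.9 to 0.5. A subject with only two post-baseline scans has a countable response with probability 0.27f, and the others with probability 0.27. With k subjects short of scan 3, the count is A + B, where A ~ Binomial(k, 0.27f) and B ~ Binomial(20 − k, 0.27).

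Example with k = 5 and f = 0.7, so 0.27f = 0.189:
- P(A = 0, 1, 2, 3) = 0.351, 0.409, 0.191, 0.044
- P(B ≤ 3, 2, 1, 0) = 0.391, 0.186, 0.058, 0.009
- P(A + B ≤ 3) = 0.351×0.391 + 0.409×0.186 + 0.191×0.058 + 0.044×0.009 ≈ 0.225

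The last column below is a simulation: 200,000 runs, Poisson accrual at 57/18 per month, confirmation at the next 6-weekly scan, and the look at the 20th subject's week-12 scan.

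| f | k = 5 | k = 6 | Simulated accrual |
|---|---|---|---|
| 0.9 | 0.187 | 0.191 | 0.19 |
| 0.7 | 0.225 | 0.237 | 0.23 |
| 0.5 | 0.267 | 0.290 | 0.28 |

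At a true ORR of 20%, the f = 0.7 case gives 0.48 to 0.49 against the stated 0.41.

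**4. Sensitivity at 27%.**
- Some first responses after scan 2: 0.32 with a 50/30/20% split over scans 1 to 3, and 0.40 with 40/30/20/10% over scans 1 to 4.
- Confirmation at exactly 28 days and a cutoff 4 weeks after the 20th subject's week-12 scan: a week-12 response is confirmed at week 12 + 4 = 16, which is inside the cutoff. The scan-2 effect disappears and the figure returns to 0.17 (0.21 with the 50/30/20% split).
- Look at week 18, or pending responses counted: 0.17 if all first responses fall at scans 1 and 2, but 0.21 and 0.25 with the two later splits. Those responses are immature at any early look.

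**The case against.** The trigger says at least 2 assessments, not exactly 2. With staggered entry most of the 20 will have three or more scans, so only about five subjects are affected. The timing split is not in the documents, and with 80% to 90% of responders seen at scan 1 the figure is only 0.19 to 0.21. Confirmation may come at 28 days, scans have a ±1 week window, and no data cutoff is stated, so an ordinary data lag could close the gap. All of this stands. It limits the size but not the direction: any response first seen after scan 1 in the late entrants can only raise the chance of missing the threshold.

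The interim is also described as descriptive. Missing the threshold leads to evaluation of other efficacy and safety data before any decision to stop permanently (9.1; SAP 6), and the study team is to assess missing data and entry delays. The study is open-label, so a pending PR would be visible to that review. This stands too.

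One could add that 9.7.3 says only *responders*. However, it also says ORR is calculated per protocol, and that definition requires confirmation. If unconfirmed responses were meant, the text needs to say so.

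Four stronger readings are tempting but not supported:
- *All 20 subjects have exactly two scans* (0.25 to 0.72 for f = 0.9 to 0.5). This ignores staggered entry.
- *The screening scan is one of the two assessments* (0.50 to 0.69 in the simulation). Table 4 does mark screening in the tumor-assessment row. But every subject needs measurable disease at screening, so the condition would shrink to one post-baseline scan. That is a strained reading, and a reason to tidy the wording rather than a measure of size.
- *The 0.17 is an arithmetic error.* It is not; it is the right tail for a fully mature count.
- *The trial would be stopped, or the final test affected.* The 0.17 is a probability of missing a threshold, not of stopping. The final analysis uses its own count, and its alpha and power calculation does not involve the interim.

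**Conclusion.** The point holds in a limited form. The interim rule applies a confirmed-response definition at a time when some confirmable responses cannot yet be confirmed, and its stated error rates ignore this. At the minimum trigger, with planned accrual, confirmation at the next scan and first responses at scans 1 and 2 only, the chance of missing the threshold at a true ORR of 27% is about 0.19 to 0.28 instead of 0.17.

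It is higher if some responses first appear later. That is plausible: Protocol 7.1.2.2 reports that about 89% of eventual responders in differentiated thyroid cancer had responded by 6 months, although that is a different tumor type and serves as context only. It is close to 0.17 with 28-day confirmation and a cutoff about 4 weeks later. The plan fixes none of these inputs. This should be corrected, but it does not undermine the design: the consequence of missing the threshold is a halt and a review.

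**What to change.** In Protocol 9.7.3 and SAP 6, specify *post-baseline* tumor assessments, and then do one of the following.

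1. For the interim tally only, count a CR or PR still awaiting its confirmatory scan as a responder. Cost: the rule becomes slightly more lenient, because some pending responses will never be confirmed.
2. Take the look once each of the 20 subjects has had the scan that could confirm a week-12 response (about week 18), or has progressed, died or ended tumor follow-up. Cost: about 6 weeks' delay, during which about 4 more evaluable subjects enter. Enrollment is not paused for the interim in any case (9.1).

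Either option restores 0.17 only if first responses fall at scans 1 and 2; with the later splits tested, 0.21 to 0.25 remains. If neither is adopted, restate 0.87, 0.41 and 0.17 for the confirmed count at the actual trigger and cutoff, with the response-timing assumption written beside them. All of these are wording changes and need no new data collection.

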9.7.4 Other Statistical/Analytical Issues

Not applicable.

9.7.5 Procedure for Revising the Statistical Analysis Plan

The SAP will be finalized prior to the database lock in this trial. Any deviation from analysis plan described in the protocol will be documented in the SAP.

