9.4.6 Blinding

The study will not be blinded.

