### 3 INTRODUCTION

The purpose of this statistical analysis plan (SAP) is to describe the procedures and the statistical methods that will be used to analyze and report results for Eisai Protocol E7080-M000-213, an Open-Label, Single-Arm, Multicenter, Phase 2 Trial of Lenvatinib for the Treatment of Anaplastic Thyroid Cancer (ATC). The focus of this SAP is on all the analyses specified in the final protocol of the study (i.e., Version 3.0 dated on 24May2016, Amendment 02), which covers the both interim analyses and final analyses. This SAP will be finalized before the database lock of study completion.

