#### 3.2 Overall Study Design and Plan

This was an open-label, single arm, multicenter, Phase 2 trial of lenvatinib (24 mg/day) to assess the efficacy and safety of lenvatinib in subjects with ATC. The study was designed primarily to provide additional efficacy and safety data for single-agent lenvatinib in a larger cohort of ATC subjects. Approximately a total of 76 subjects was planned to be enrolled into this study (i.e., signed informed consent) to be sure that out of the 76 subjects there would be 57 subjects confirmed with ATC for the purpose of efficacy analyses. Also one interim analysis was planned to be performed after the first 20 evaluable subjects completed at least 2 tumor assessments or discontinue treatment due to any reason. While waiting for the

interim analysis results the enrollment would not be suspended so that no enrollment gap was in the study for the interim analysis. From the interim analysis the enrollment would be halted if the number of responders was 3 or less (ORR  $\leq$ 15%, according to Response Evaluation Criteria in Solid Tumors (RECIST) 1.1), and the safety and efficacy data would be further evaluated before making the decision of stopping the study permanently.

This study would consist of the following three phases and the corresponding procedures/assessments to each was presented as Table 4 in the final protocol of the study in details, where as shown a 28-days during the treatment period was considered as one cycle of treatment and used for study related visits/assessments:

- The **Pretreatment Phase:** including Screening period from Day -21 prior to the first study treatment of lenvatinib start. All analyses related baseline assessments would be defined as the last assessment obtained during this phase for each.
- The **Treatment Phase:** starting from the time of the first lenvatinib administration till the end of last lenvatinib administration. Subjects would be treated with lenvatinib dose of 24 mg once daily by oral administration, or dose following protocol on treatment adjustment.
- The **Posttreatment Phase:** starting after the last study dose, including End of Treatment visit (i.e., within 30 days of last dose), survival follow-ups (i.e., every 12 ( $\pm$ 1) weeks after End of Treatment visit).

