### 5.2.5 Prior and Concomitant Therapy

All investigator terms (verbatim terms) for medications recorded in the CRF will be coded to an 11-digit code using the World Health Organization Drug Dictionary (WHO DD) (WHODDMAR2018). The number (percentage) of subjects who took prior and concomitant medications will be summarized in FAS by Anatomical Therapeutic Chemical (ATC) class, and WHO DD preferred term.

Prior medications are defined as medications that stopped before the first dose of study drug. Concomitant medications are defined as medications that (1) started before the first dose of study drug and were continuing at the time of the first dose of study drug, or (2) started on or after the date of the first dose of study drug up to 28 days after the subject's last dose. All medications will be presented in subject data listings.

Frequencies [n (%)] of previous anti-cancer procedures will be summarized similarly by system organ class and preferred term. In addition, previous anti-cancer medications will be summarized in terms of number of prior regimens, duration of last therapy, best response for last therapy, time from end of last therapy to first dose, and indication of previous medication

(neoadjuvant/adjuvant/metastatic/unknown). The following data on radiotherapy will be summarized: time from last radiotherapy to first dose, site of previous radiotherapy, progression of tumor lesion at the site since radiotherapy (yes/no), and number of all prior radiotherapy treatments.

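### One SAP covers the interim and final analyses of an unblinded single-arm trial but is finalized only before final lock, which leaves the secondary-endpoint population and test order exposed to late choice

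*Protocol*

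**What the plan says.** **Timing.** Protocol 9.7.5 has two sentences: "The SAP will be finalized prior to the database lock in this trial" and "Any deviation from analysis plan described in the protocol will be documented in the SAP". It does not ask that the protocol-specified result be reported alongside a changed one. SAP 3 describes a single plan, "which covers the both interim analyses and final analyses. This SAP will be finalized before the database lock of study completion". Neither document describes an interim SAP or a sign-off before the interim.

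**Visibility of results.** Protocol 9.4.3 describes one arm without randomization, and 9.4.6 adds "The study will not be blinded". Response and progression are read by the investigator (Protocol 9.5.1.3, SAP 5.1). At the interim on 20 evaluable subjects, "The study team will define the datasets for the interim analysis", and "The study statistician will perform the interim analysis, which includes calculating ORR per protocol" (Protocol 9.7.3). No separation between that work and later SAP writing is described.

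**Secondary endpoints.** Protocol 9.7.1.2 makes the EAS (centrally confirmed anaplastic thyroid cancer) the primary efficacy population, and 9.7.1.9 places the secondary endpoints there. Protocol 9.7.1.6.4 adds an efficacy analysis in the FAS. Protocol 9.7.1.6.2 has the secondary endpoints analyzed in sequence. SAP 5.4.2 puts all secondary efficacy analyses in the FAS. SAP 5.3.3 makes no multiplicity adjustment for them and does not restate the order. SAP 7 lists two changes only: treatment duration in months, and the dropped biomarker analyses.

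**The concern.** Finalizing a SAP before lock protects an analysis when outcomes stay hidden until lock. Here every outcome belongs to the one treatment arm and is known at the site as it arrives, and an aggregate response rate is computed partway through. A plan that is still open at that point can be shaped by what has been seen.

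The secondary claims depend on fixed limits: the lower 95% confidence bound must exceed 50% for 12-week PFS and 44% for 6-month OS (Protocol 9.7.1.6.2). The nominal error of those comparisons holds only if the population and the order of testing were settled independently of the results. The one safeguard in 9.7.5 is that departures be documented in the SAP. SAP 7, the section for changes to planned analyses, omits the two departures that bear most on these claims.

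**Working it through.** **1. The plan's own figures.** Inputs from Protocol 9.7.2 and 9.7.3: n = 57, null ORR 10%, alternative 27%, one-sided 0.025, and an interim halt at 3 or fewer responders among 20.
- The smallest r with P(X ≥ r | 57, 0.10) ≤ 0.025 is r = 11, since r = 10 gives 0.0548 and r = 11 gives 0.0242. Power is P(X ≥ 11 | 57, 0.27) = 0.9321, against 0.932 stated.
- P(X ≤ 3 | 20, p) = 0.867, 0.411 and 0.170 at p = 10%, 20% and 27%, against 0.87, 0.41 and 0.17 stated.
- Enrollment is 57 / 0.75 = 76, as stated.

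All reproduce. The point concerns governance, and no stated figure is wrong.

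**2. What is fixed and what moved.**

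| Item | Protocol | SAP | In SAP 7? |
|---|---|---|---|
| Primary: ORR, EAS, exact test, 0.025 | 9.7.1.1.1, 9.7.1.2, 9.7.1.6.1, 9.7.2 | Same (5.1.1, 5.2.1, 5.4.1) | Not needed |
| Interim: 20 subjects, 3 or fewer | 9.7.3 | Same (6) | Not needed |
| Secondary population | EAS (9.7.1.2, 9.7.1.9) | FAS (5.4.2) | No |
| Secondary test order | Sequential (9.7.1.6.2) | No adjustment, order not restated (5.3.3) | No |

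**3. What late choice of population could cost.** Assumptions: 57 EAS subjects; 76 FAS subjects, so that all 76 enrolled are treated and 76 − 57 = 19 are unconfirmed; the same true rate p0 in both groups; no censoring before the landmark, so that the Kaplan-Meier estimate is a proportion. The documents name Greenwood's formula but no transformation of the interval, so two bounds are shown.

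Plain bound: claim if p̂ − 1.96·√(p̂(1 − p̂)/n) > p0. For PFS in the EAS, 36/57 gives 0.6316 − 1.96 × 0.0639 = 0.5064, and 35/57 gives 0.4877, so 36 is the smallest count that succeeds. The other limits are 47/76 (PFS, FAS), 33/57 (OS, EAS) and 42/76 (OS, FAS).

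Log-log bound: claim if p̂^exp(1.96·se/(p̂·|ln p̂|)) > p0, where se is the same root term. The limits are 37/57 and 48/76 for PFS, and 33/57 and 43/76 for OS.

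With EAS limit a and FAS limit b, the chance of a false claim from the better population is the sum over x of Bin(x; 57, p0) × [1 if x ≥ a, otherwise P(Bin(19, p0) ≥ b − x)]. Exact results:

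| Endpoint and bound | EAS only | FAS only | Better of the two |
|---|---|---|---|
| 12-week PFS, p0 = 0.50, plain | 0.0314 | 0.0252 | 0.0413 |
| 6-month OS, p0 = 0.44, plain | 0.0243 | 0.0317 | 0.0410 |
| 12-week PFS, p0 = 0.50, log-log | 0.0166 | 0.0143 | 0.0231 |
| 6-month OS, p0 = 0.44, log-log | 0.0243 | 0.0185 | 0.0317 |

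**The case against.** **The main analysis is already protected.** The primary endpoint, population, test, level and interim threshold stand in the protocol and are carried over intact. The interim is descriptive and can only halt enrollment, so it cannot yield an efficacy claim. Protocol 9.7.1.6.2 also sets the main PFS censoring rules. All of this stands, and it confines the point to the secondary endpoints.

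**The SAP cannot freely override the protocol.** Protocol 9.7.5 speaks of documented deviations, and Protocol 11.1 requires a written amendment or administrative change for any change to the protocol. The protocol also promises both EAS and FAS results. This is fair as to intent, but SAP 5.4.2 replaces the population for the secondary endpoints and SAP 7 does not record it. It can also be said that a fixed sequence needs no alpha adjustment, so SAP 5.3.3 might coexist with the protocol's order. The SAP does not say so.

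**A reader might infer a larger inflation.** If the 19 unconfirmed subjects are assumed to do 10 points better, the better-of-two rates become 7.0% (PFS) and 8.1% (OS). These do not measure late choice. With the FAS fixed in advance, the same scenario gives 6.3% and 7.8%, because the true FAS rates are then (57 × 0.50 + 19 × 0.60)/76 = 52.5% and (57 × 0.44 + 19 × 0.54)/76 = 46.5%, above the limits. If the 19 do 10 points worse, the plain-bound figures are 3.3% and 2.7%. The documents give no rate for this group.

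**A reader might infer that the rules were written after the results.** The SAP describes the design partly in the past tense and names the drug dictionary "WHODDMAR2018", against a protocol dated May 2016 and a planned study of about 24 months. This is circumstantial. A dictionary version does not date a population rule, the prospective protocol itself slips into the past tense on ECGs (9.7.1.8.5), and the SAP's date is not in the text available here.

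**Signing before the interim is not a full cure.** Sites know individual outcomes from the first treated subject. That is true, but the interim is the first planned aggregate look, and so a natural date by which to fix the rules.

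**Conclusion.** The point holds as a modest governance weakness in the secondary analyses. One SAP is meant to govern the interim but need not be final until the end of an unblinded trial. Two departures on the secondary endpoints, EAS to FAS and sequential order to no adjustment, are missing from SAP 7. The documents establish that choice after results was possible. They do not establish that it occurred, and they do not put the primary analysis in doubt.

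The size is small. Under equal true rates and no early censoring, choosing the better population adds 1.0 point for 12-week PFS (3.1% to 4.1%) and 1.7 points for 6-month OS (2.4% to 4.1%) with a plain Greenwood bound. With a log-log bound the rises are from 1.7% to 2.3% and from 2.4% to 3.2%. Part of the plain-bound PFS figure is the bound itself, which already exceeds 2.5% in the EAS alone. The effect of the dropped test order was not quantified.

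**What to change.** - **Protocol 9.7.5 and SAP 3:** state that the SAP is finalized and signed before data are extracted for the interim analysis.
- **Later departures:** keep the protocol-specified analysis (EAS, sequential order) as the reported result for the secondary endpoints, with the SAP's version labelled supplementary.
- **SAP 7:** list every departure, including EAS to FAS and the multiplicity change, each with its date and the outcome data already seen at that date.

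If the interim has already taken place, the second and third items can still be done.

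The cost is earlier SAP writing and a few analyses run twice. Patients, sites, sample size, alpha and power are unaffected.
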